#### 4.6. Control Group Labeling

With protocol version 5 on, drug supplies for the control group included tablets containing a urinary discolorant (MTC), 4 mg, dosed at an average frequency of two tablets per week (see Sections 1.3 and 2.1). This means, that most of the subjects randomized to placebo/control received at least one dose of MTC. The sponsor will provide an Excel file to Cytel, which will list the subjects who received placebo only and subjects who transitioned from placebo to MTC 8 mg/week. All other control group subjects will have received MTC 8 mg/week.

In the analysis, a few tables will present subjects who received placebo only separately from subjects who received at least one dose of MTC, which is then highlighted in the respective section of this SAP. In this case, the following treatment group labels will be used: "Placebo Only" and "MTC 8 mg/week".

For other analyses in which subjects randomized under a protocol version before version 5 are included (e.g., ITT population, see Section 3.1.1), the label for the control group will be "Placebo and/or MTC 8 mg/week", and for the analyses in which subjects randomized under a protocol version before version 5 are not included (e.g., ITTv5 population), the label for the control group will be "MTC 8 mg/week".

In the subject data listings control group subjects will be labeled as "Placebo Only" and "MTC 8 mg/week", respectively.

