The drug accountability sheet therefore has several rows for one dispensed visit/kit. It monitors the initial creation and every update done to it. To analyze the data, the most recent information will be used, which is the last entry, by using the sorting of the raw data file, of each kit.

The following information will be summarized descriptively by treatment group and overall, whereas subjects randomized to placebo/control will be analyzed separately by subjects receiving only true placebo and subjects receiving at least one dose of MTC:

- Total duration of exposure (in weeks): (last dose date – first dose date + 1)/7
- Total duration of treatment (in weeks), which excludes days in which dose was interrupted
- Mean daily dose: Total of administered dose during the duration of exposure, relative to the total duration of exposure

Sponsor:	TauRx Therapeutics Ltd.		
Protocol:	TRx-237-039		
Document Version No.:	3.0	Document Date:	07-JUN-2023

- Total subject-years of exposure: sum of total exposure in years

$$\frac{1}{365.25} \sum_{\text{subjects}} \frac{\# \text{tablets taken during db phase}}{\# \text{tablets planned during db phase}} * \text{total duration of exposure (days)}$$

- Compliance: # Tablets taken / # tablets planned until Week 52 (or until early study drug termination). Including frequency and percentage of subjects with <80% and >120% compliance. A compliance flag will be re-calculated together with the actual compliance figure.
- Frequency and percentage of subjects with dose interruptions
- Frequency and percentage of subjects in the duration of exposure categories (with categories based on the scheduled day for each planned visit, see Table 5: 1 day, 2 to 29 days, 30 to 92 days, etc.), based on total duration of exposure, including interruption days

This summarization will be done for the Safety population, but also repeated restricted to the subjects randomized before protocol version 5.0, and restricted to the subjects randomized under or after protocol version 5.0 (Safetyv5).

Subject data listings will encompass dosing, drug accountability, and compliance. Any doses that are other than that randomized will be flagged and the protocol version under which the subject had been randomized will be given.

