#### 5.12.2. Adverse Events

Adverse events (AEs) will be coded using the MedDRA version 20.1 and are displayed in tables and listings using SOC and PT.

Treatment emergent AEs (TEAE) are defined as AEs with:

- Onset after first dose of study drug or
- Worsen in intensity after first dose of study drug or
- Worsen in treatment relationship after first dose of study drug

Based on the Safety population, a time-to-event analysis (event: any TEAE) will be performed using the model as described in Section 5.9.5). The time-to-first TEAE will be calculated as date of onset – date of first dose + 1, and subjects with no TEAE will be censored at the time of study discontinuation.

AEs are summarized by subject incidence rates, therefore, in any tabulation, a subject contributes only once to the count for a given AE (SOC or PT, most related occurrence, or most intense occurrence) regardless the number of episodes.

The total number of subjects and the numbers stratified by MedDRA SOC and PT, along with the corresponding percentage, with the following AE will be derived and summarized by treatment group and overall:

Sponsor:	TauRx Therapeutics Ltd.		
Protocol:	TRx-237-039		
Document Version No.:	3.0	Document Date:	07-JUN-2023

- Any TEAE (separate columns for true placebo and MTC)
- Any TEAE with an onset of Day 1 (separate columns for true placebo and MTC), complemented by a subject data listing
- Any TEAE (categorized by severity, and separate columns for true placebo and MTC), repeated for the Safetyv5 population.
- Any TEAE (categorized by severity) which occurred within two weeks after any COVID-19 vaccination (separate columns for true placebo and MTC)
- Any TEAEs assessed by the Investigator as related to treatment (i.e., related or possibly related) (separate columns for true placebo and MTC)
- Any TEAEs severe in intensity and assessed by the Investigator as related to treatment (as defined above) (separate columns for true placebo and MTC)
- Any TEAE that resulted in interruption or discontinuation of study drug (presented separately and combined) (separate columns for true placebo and MTC)
- Any SAE (separate columns for true placebo and MTC)
- Any serious adverse reaction (SAR), which are the SAEs judged to be possibly related or related to the study drug by the Investigator (separate columns for true placebo and MTC)
- Malignancies other than non-melanoma skin cancers (separate columns for true placebo and MTC)

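### Control subjects who switched from true placebo to MTC are reported wholly under MTC in the split safety tables, which misattributes their placebo-period data and leaves Placebo Only as a subset selected after randomization

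*SAP*

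**What the plan says.** SAP 4.6 (Control Group Labeling) explains that MTC tablets were added to control supplies from Protocol Version 5.0, so that "most of the subjects randomized to placebo/control received at least one dose of MTC". A sponsor file will "list the subjects who received placebo only and subjects who transitioned from placebo to MTC 8 mg/week"; every other control subject is taken to have received MTC. Where the control group is divided, the tables "present subjects who received placebo only separately from subjects who received at least one dose of MTC". Only two column labels are provided, Placebo Only and MTC 8 mg/week.

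SAP 5.12.1 applies the same rule to exposure and compliance, dividing control into "subjects receiving only true placebo and subjects receiving at least one dose of MTC".

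SAP 5.12.2 applies it to adverse events. The first entry in its list reads "Any TEAE (separate columns for true placebo and MTC", and the same column instruction appears on 14 adverse-event tables. They include Day 1 onset, severity, relatedness, interruption or discontinuation, SAEs, malignancies, the TauRx AE groupings and the AESIs. The first criterion for a treatment-emergent event is "Onset after first dose of study drug or", with worsening in intensity or in attribution after that dose as alternatives. Within a table, "a subject contributes only once to the count for a given AE".

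Two other provisions bear on this. SAP 3.1.1 assigns a Safety-population subject who received different doses to the predominant treatment by number of doses. SAP 6.13.2, for control subjects who move to HMTM in the open-label phase, leaves out events that precede the first HMTM dose.

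**The concern.** True placebo is the only control exposure in the trial free of the MT moiety, and SAP Version 3.0 added the division of the control group so that it could be seen apart. A reader of the tables will take the Placebo Only column as that reference and the MTC column as what happened on MTC.

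The rule does not deliver this for subjects who switched. One MTC tablet moves a subject's whole double-blind record into the MTC column, including months when the subject took only placebo. Switching also requires staying on study long enough to receive Version 5.0 supplies. Placebo Only is therefore defined by something that happens after randomization. At stake is how the descriptive safety tables are read. The efficacy conclusions are not at stake.

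**Working it through.** The plan states no figure on this point, so there is none to reproduce. The first two steps rest on the text alone; the sizes after them are illustrations.

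**1. The text.** 4.6 acknowledges subjects who switched, gives two labels, and divides by any MTC dose, so those subjects can only be under MTC. 5.12.2 starts the event clock at the first dose of study drug. No section dates events against the first MTC dose, ends placebo time at the switch, or gives these subjects their own column.

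**2. A case that needs no assumption.** One of the 14 tables shows treatment-emergent events with onset on Day 1. A subject who went from placebo to MTC was on placebo on Day 1. Any such event preceded MTC and is still tabulated as MTC.

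**3. Group sizes.** Planned enrollment is about 500, of which 450 is under Version 5.0 or later (SAP 2.1), so about 500 − 450 = 50 came earlier. Earlier allocation to placebo was 2 in 5 or 1 in 2 (SAP Table 1), giving 50 × 2/5 = 20 to 50 × 1/2 = 25 control subjects. I assume that those who switched come from this group; SAP 6.1 mentions subjects who re-consented to Version 5 or later after randomization. Let k be the number who switched, with planned MTC-column size 200 + k. The fraction that switched is assumed.

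| Assumed fraction | k | Placebo Only | k / (200 + k) |
|---|---|---|---|
| 25% | 5 to 6.25 | 15 to 18.75 | 2.4% to 3.0% |
| 50% | 10 to 12.5 | 10 to 12.5 | 4.8% to 5.9% |
| 75% | 15 to 18.75 | 5 to 6.25 | 7.0% to 8.6% |

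**4. Placebo time inside the MTC column.** With a switch at month s of 12 and full follow-up, the share is k·s / [12(200 + k)]. Lowest: 5 × 6 / (12 × 205) = 1.2%. Highest: 18.75 × 9 / (12 × 218.75) = 6.4%.

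**5. First events on placebo among those who switched.** Under a constant hazard with 12-month incidence p, the share of first events before the switch is [1 − (1 − p)^(s/12)] / p. For p = 50% and s = 6 this is 0.293 / 0.50 = 59%. For p from 5% to 80% it is 51% to 69% with a switch at month 6, and 76% to 88% at month 9. All of these count under MTC.

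**6. Direction for events that do not end participation.** Planned double-blind treatment was 6 or 9 months before Version 5.0 and 12 months from it (SAP Table 1). With one constant hazard and 50% incidence at 12 months, crude incidence is 1 − 0.5^(6/12) = 29% at 6 months and 1 − 0.5^(9/12) = 41% at 9 months. Placebo Only looks better than MTC at equal risk.

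**7. Direction for events that end participation.** A subject who stops on placebo because of an event never switches. Take 24 early control subjects, of whom 12 switch and 10% (2.4) stop for an event beforehand (all assumed). Placebo Only shows 2.4/12 = 20%, against 2.4/24 = 10% in the whole group. Placebo Only now looks worse.

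**8. Competing rule.** Control subjects on MTC take 2 MTC tablets among 4 × 7 = 28 a week, or 7%. The predominant-dose rule in 3.1.1, applied to these columns, would put control subjects under placebo; 4.6 puts them under MTC.

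**The case against.** The strongest reply is that these are descriptive tables with safeguards around them. No formal testing of event incidence is planned. Primary efficacy uses the Version 5.0 populations with a single control group. The severity and AE-grouping tables are repeated for Safetyv5, which excludes subjects randomized earlier. Exposure is repeated for earlier and later subjects separately, and duration and subject-years are shown by the same division, so shorter follow-up in Placebo Only would be visible. Time to first treatment-emergent event is analyzed with censoring for the overall control comparison. Listings give randomization version, re-consent dates, dose dates and all events, so individuals can be traced.

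Most of this stands, and it limits the point. It does not remove it. The Safetyv5 repeats clean the MTC column, but they cannot restore the placebo reference, and among the 14 divided tables only those two are named for repetition. Subject-years follow the same any-dose rule, so placebo time of those who switched is in the MTC denominator.

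A reader might infer that, at equal risk, MTC must look worse than true placebo and that HMTM against true placebo is distorted the same way. The documents do not support that: steps 6 and 7 give opposite directions, and step 7 bears directly on the table of events leading to interruption or discontinuation. Nor are both columns mixed. Placebo Only is free of MTC; only the MTC column mixes the two. It is also fair to say that, with at most about 20 to 25 planned subjects ever on true placebo, the reference stays imprecise under any rule.

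**Conclusion.** The rule as written misattributes placebo-period events and exposure in 14 adverse-event tables and the exposure summary, and it defines Placebo Only by a post-randomization event. That follows from the text alone.

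The net direction is not fixed: non-terminating events tend to be under-counted in Placebo Only, while events that lead to withdrawal are over-represented there. The size cannot be determined, because the documents give neither the number who switched nor the switch dates, and the 50 early subjects are a planned figure. Under the assumed range, the loss of subjects from Placebo Only is the larger effect and contamination of the MTC column the smaller one. That the subjects left in Placebo Only had shorter follow-up is probable from the earlier 6- and 9-month designs, but it is not stated. The consequence is confined to descriptive safety reporting and is worth correcting because the repair is nearly free.

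**What to change.** In SAP 4.6, 5.12.1 and 5.12.2, show control subjects who switched in a third column, Placebo then MTC, in every exposure and adverse-event table that divides the control group. Print subject-years beside the counts in those columns. The file described in 4.6 already identifies these subjects.

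State which rule governs the columns: the any-dose division in 4.6 or the predominant-dose assignment in 3.1.1.

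Optionally, add each such subject's first-MTC date to the file and flag in the listings whether each event began before or after it. This would parallel what 6.13.2 does for the move from control to HMTM.

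The cost is SAP wording and one extra small column; the optional step adds one date per subject. Full attribution of events by time would be heavier. It needs a second reference point for events that worsen and an exception to counting each subject once, and the third column avoids both.

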#### 4.7. Subject Data Listings

Subject data listings of all documented data of interest will be provided (see efficacy, safety, and exploratory analysis sections).

Sponsor:	TauRx Therapeutics Ltd.		
Protocol:	TRx-237-039		
Document Version No.:	3.0	Document Date:	07-JUN-2023

For the efficacy endpoints the following listings will be prepared: one showing the total score of the scales (ADAS-cog11, ADAS-cog13, ADCS-ADL23, Composite Scale, and COVID-19 Composite Scale), one showing the MRI parameters and another one showing the F-FDG-PET parameters. These listings will be accompanied by:

- the information under which protocol version the subject has been randomized,
- a flag for subjects who are excluded from the respective MITT population,
- a flag for assessments that are not potentially confounded by intercurrent illnesses, COVID-19, and concomitant medications (which includes assessments after initiation of an AchEI and/or memantine) as identified during the BDRM,
- a flag for “off treatment” assessments that are after 14 days after the withdrawal of study treatment, or after 14 days after the beginning of a dose interruption and before the restart of study drug intake,
- a flag if the assessment was done remotely,
- the upscaled value,
- a flag indicating a response, and
- a flag indicating a decline.

In addition, for the scales, the individual items and any computed subdomains/ scores etc. will be listed. If feasible, ADAS-cog11 and ADAS-cog13 can be listed together. For MMSE and CDR separate listings will be provided, too.

Further subject data listings are described in their respective sections (e.g., subject disposition).

#### 4.8. Summary Statistics

To complete the efficacy analysis, which is described in the following sections, summary statistics will be tabulated by visit and treatment group using observed data (after upscaling is applied); for the absolute values, and the change from Baseline, based on the respective analysis populations. This will be repeated for subjects with treatment initiation of AchEI and/or memantine (post-hoc, if sample size is sufficiently high), and for withdrawals from study treatment but remaining in the study (TOTOS, see Section 4.4), separately, for selected primary and secondary endpoints (ADAS-cog11, ADCS-ADL23, MRI whole brain volume, F-FDG-PET temporal lobe). If the number of subjects with treatment initiation of AchEI and/or memantine is less than five, a separate subject data listing is enough. Summary statistics for sensitivity analysis will be done post-hoc, if of interest.

If applicable, the absolute values, change from Baseline, and treatment difference (with its 95% confidence intervals), between the HMTM active group(s) and control, based on the least squares

Sponsor:	TauRx Therapeutics Ltd.		
Protocol:	TRx-237-039		
Document Version No.:	3.0	Document Date:	07-JUN-2023

---

means (LSM) from the corresponding MMRM or ANCOVA model, will be presented by visit (e.g., see Section 5.9.2.1).

The number and percentage of affected (missing or likely impacted) assessments by COVID-19 will be summarized by endpoint and visit, and further by treatment group and overall, using the information from the respective eCRF *Covid-19 Impact Assessment*. From this eCRF the reason(s) why the study visit was affected, e.g., *Subject unable to attend clinic visit*, will be analyzed in the same way. The denominator is the number of subjects who were still on study for the respective visit.

Sponsor:	TauRx Therapeutics Ltd.		
Protocol:	TRx-237-039		
Document Version No.:	3.0	Document Date:	07-JUN-2023

## 5. STATISTICAL ANALYSIS OF DOUBLE-BLIND TREATMENT PHASE

In the following, *decline* is defined as a change into the direction of greater impairment. An *on-treatment visit*, and their corresponding assessments, is defined as a visit where a subject was on investigational product (within the last 14 days) and not on any AchEI and/or memantine (except short-term use). This means, in case of a longer dose interruption a visit can be off-treatment if the subject was not on-treatment within the last 14 days of the visit.

### 5.1. Primary Efficacy Analysis

There are two co-primary efficacy endpoints for this trial: Baseline adjusted decline in ADAS-cog11 and Baseline adjusted decline in ADCS-ADL23 from Baseline at Week 52. Repeated measurements on these endpoints scheduled at Weeks 13, 26, 39, and 52 will be treated using a mixed effects model (see Section 5.9). Suppose  $\mu_{ADAS-cog11,T}$  and  $\mu_{ADCS-ADL23,T}$  are the means of decline at Week 52 for the treated arm and  $\mu_{ADAS-cog11,C}$  and  $\mu_{ADCS-ADL23,C}$  are the corresponding means for the control arm, then the global null and the alternative primary efficacy hypotheses can be written as:

$H_0: \mu_{ADAS-cog11,T} = \mu_{ADAS-cog11,C}$  OR  $\mu_{ADCS-ADL23,T} = \mu_{ADCS-ADL23,C}$  ; versus

$H_1: \mu_{ADAS-cog11,T} \neq \mu_{ADAS-cog11,C}$  AND  $\mu_{ADCS-ADL23,T} \neq \mu_{ADCS-ADL23,C}$  .

Thus, the global null versus alternative is a Union-Intersection Test (UIT) which requires both co-primary endpoints to meet statistical significance at the 5% two-sided level of significance for the global null hypothesis to be rejected.

### 5.2. Multiple Comparisons/Multiplicity

In the double-blind treatment phase, the primary comparison is between HMTM 16 mg/day and control, based on subjects randomized under study protocol version 5.0 or higher.

Both co-primary endpoints must reach significance based on the use of a two-sided test at the alpha=0.05 level of significance for HMTM 16 mg/day to be designated as superior to control. This is because the global null hypothesis is only rejected if and only if the null hypothesis for each of the two co-primary endpoints are rejected. Furthermore, since the efficacy endpoints are primarily analyzed based on two different analysis populations (ITTv5, and the respective MITTv5), the pre-defined sequence is MITTv5 before ITTv5. ITT and MITT populations will be analyzed in the framework of sensitivity analyses.

Therefore, no multiplicity adjustment is necessary.

Sponsor:	TauRx Therapeutics Ltd.		
Protocol:	TRx-237-039		
Document Version No.:	3.0	Document Date:	07-JUN-2023

### 5.3. Sample Size Justification

Sample size estimations to achieve 90% power (two-sided alpha = 0.05) to detect a difference between HMTM 16 mg/day and true placebo have been performed for the two co-primary clinical endpoints. These assume a withdrawal rate of 20% to 25% over 52 weeks. The study sample size – here restricted to subjects randomized under protocol version 5.0 or higher as this is the primary analysis population – of approximately 450 subjects (approximately 200 subjects in each treatment group, with a further 50 subjects for secondary analyses of an HMTM 8 mg/day group) is based on the ADCS-ADL23 as a larger sample size is required to achieve the target power.

Based on an estimated decline in ADCS-ADL23 over 52 weeks in the control arm of 7.7 units with an estimated SD of 8.5 units, the study will have approximately 93.2% power (two-sided alpha=0.05) to detect a reduction in decline of 3.4 units or more. The 3.4 units are motivated by an estimated treatment effect of  $5.0 \pm 1.6$  (mean  $\pm$  standard error) units in the pooled studies TRx-237-005/ TRx-237-015.

Based on an estimated decline in ADAS-cog11 over 52 weeks based on pooled information from Studies TRx-237-005 / TRx-237-015 in the control arm of 6.5 units with an estimated SD of 5.9 units, 200 subjects per treatment arm provide approximately 96.7% power (two-sided alpha=0.05) to detect a reduction in decline of 2.6 units or more. The 2.6 units represent a conservative value as the estimated treatment effect based on pooled Studies TRx-237-005 / TRx-237-015 is  $5.2 \pm 1.3$  (mean  $\pm$  standard error) units.

### 5.4. Protocol Deviations

Protocol deviations from the double-blind treatment phase will be analyzed as described in Section 3.2.

### 5.5. Visit Windows

Since data might be documented under a wrong label (as a wrong visit) within the EDC system, all data will be (re-)assigned to a visit according to the column *Intervals for analysis* in Table 5.

Furthermore, if a subject has multiple values for a parameter within a visit window, the “worst” value will be used for that visit window summary (see Appendix 12.3), for efficacy endpoints the closest to the scheduled visit will be used (if two have the same distance from the scheduled visit the later one will be used, and if two have the same day, the Sponsor will provide a file, which identifies the value to be used in the analysis). For the double-blind treatment phase, priority at Week 52 is given to assessments that took place before initiation of the open-label treatment in case there are multiple values for them within the visit window.

Sponsor:	TauRx Therapeutics Ltd.		
Protocol:	TRx-237-039		
Document Version No.:	3.0	Document Date:	07-JUN-2023

As an exception, for the analysis of the double-blind treatment phase, a delayed Week 52 F-FDG-PET or MRI assessment will be included in the double-blind treatment phase even if it has been done within 14 days after first dose of the open-label treatment phase drug. In addition, the eye exam is eligible for the double-blind treatment phase, if it was performed until the end of the Week 52 protocol-specified visit window. For all other efficacy endpoints and safety information only assessments before the first dose of the open-label treatment phase or if assessments were done on the same day of the first open-label phase treatment are eligible for analysis of double-blind treatment phase data.

